Definition of Dose-limiting Toxicity (DLT):	
Dose-limiting toxicities (DLTs) are defined as AEs that occur during Cycle 1, are classified as possibly or probably related to the study drug, and meet one of the following CTCAE v4.03 criteria below.

Hematologic Toxicities:	
 • Grade 4 neutropenia lasting >7 days • Grade ≥ 3 neutropenia with fever • Grade 4 thrombocytopenia • Grade ≥ 3 thrombocytopenia lasting more than 7 days or associated with clinically significant bleeding • Grade 4 anemia
Other Toxicities:	
 • Any \geqGrade 3 (AE or laboratory) toxicity despite adequate supportive care/medical management except for the following: 
 • Grade ≥ 3 nausea, vomiting, or diarrhea that resolves to Grade ≤ 2 within 72 hours, with or without medical intervention or prophylaxis because this would not be considered treatment-limiting in an oncology population • Grade 3 fatigue that resolves to \leqGrade 2 within 14 days because this would not be considered treatment-limiting in an oncology population • Grade ≥ 3 asymptomatic changes in alkaline phosphatase, hypomagnesemia, hyperglycemia, or hypophosphatemia that are felt by the investigator to be clinically insignificant • Grade 3 increases in transaminases confirmed upon repeat testing lasting ≤ 5 days • Any other Grade ≥ 3 toxicity (except those noted above) for which either the Principal Investigator or Sponsor deems further dose escalation inappropriate

For Part 1 and Parts 2b and 2e in the absence of a DLT, patients must complete the first cycle of treatment (28 days) in order to be considered evaluable for DLT. Patients who discontinue for any reason other than a DLT or Grade ≥ 2 toxicity and have received less than 21 of 28 days of dosing will not be considered evaluable for DLT and will be replaced. This will be evaluated by the Study Committee.
 
In the event of a fatal DLT that is possibly or probably attributed to study drug, further accrual to that dose level will be suspended pending review by the study committee. The Study Committee will review the available data regarding the event and provide recommendations.
	
Safety and Tolerability Assessments:	
Safety and tolerability assessments will include physical examinations, vital signs, 12-lead electrocardiograms, AEs, hematology, complete chemistry panel, coagulation, and urinalysis.

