9.2.2 Dose Escalation Rules

Dose escalation will occur in accordance with the rules listed below.

- The DLT window is 28 days.
- A minimum of 3 patients will be initially enrolled per cohort.

- If 1 of the first 3 patients enrolled in a given cohort experiences a DLT, at least 3 additional patients will be enrolled in that cohort.
- If less than one-third of evaluable patients in a given cohort experiences a DLT (e.g., DLTs in 0 of 3 or \leq 1 of 6 patients), escalation will proceed to the next higher dose level.
- If a DLT is observed in one-third (e.g., 33%) or more of patients (e.g., 2 or more of up to 6 patients), the dose combination at which this occurs will be considered intolerable and the MTD will have been exceeded.
- The highest dose level at which 0 or 1 of 6 experience a DLT will be declared the MTD. If only 3 patients were initially evaluated at that dose level, an additional 3 patients will be enrolled to evaluate for DLTs at that dose level.
- After dosing has been completed in each cohort, safety and PK data (as applicable) will be reviewed by and dose escalations decisions made by the Sponsor, and investigators and study staff from all participating sites.
- If \geq 2 patients in one cohort experience \geq Grade 2 toxicities that are considered possibly or probably related to PLX9486, PLX9486 combined with PLX3397, or PLX9486 and sunitinib within the first 28 days, the study committee will determine the dose escalation increment after review of the safety, PK, and PD data.

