9.3 Definitions of Dose-limiting Toxicity

Dose-limiting toxicities (DLTs) are defined as AEs that occur during Cycle 1, are classified as possibly or probably related to the study drug, and meet one of the following CTCAE v4.03 criteria below. DLTs will be evaluated for each cohort and for each dosing schedule. Toxicities that occur during Cycle 2 or later will be reviewed, and their impact on dose-escalation and dosing frequency will be assessed.

In each cohort, to maximize safety, there will be a 24-hour delay between the first subject enrolled and later subjects enrolled. .

Subjects who are considered in dose-escalation decisions are not allowed dose reductions during the DLT assessment window. Subjects who withdraw from the study prior to completing Cycle 1 for any reason other than a DLT will be replaced. Patient numbers must not be re-used.

A subject who experiences a DLT may remain in the trial and continue receiving study drug at a lower dose if the investigator deems the potential benefit outweighs the risk and that the subject is not eligible for, and/or interested in, an alternative therapy after consultation with the Medical Monitor.

Hematologic Toxicities

- Grade 4 neutropenia lasting >7 days
- Grade ≥ 3 neutropenia with fever
- Grade 4 thrombocytopenia
- Grade ≥ 3 thrombocytopenia lasting more than 7 days or associated with clinically significant bleeding
- Grade 4 anemia

Other Toxicities

- Any \geq Grade 3 (AE or laboratory) toxicity despite adequate supportive care/medical management except for the following:
 - Grade ≥ 3 nausea, vomiting, or diarrhea that resolves to Grade ≤ 2 within 72 hours, with or without medical intervention or prophylaxis because this would not be considered treatment-limiting in an oncology population
 - Grade 3 fatigue that resolves to \leq Grade 2 within 14 days because this would not be considered treatment-limiting in an oncology population
 - Grade ≥ 3 asymptomatic changes in alkaline phosphatase, hypomagnesemia, hyperglycemia, or hypophosphatemia that is felt by the investigator to be clinically insignificant
 - Grade 3 asymptomatic increases in transaminases (AST, ALT) confirmed upon repeat testing which resolves to \leq Grade 2 within <5 days
- Any other Grade ≥ 3 toxicity (except those noted above) for which the Principal Investigator or Sponsor deems further dose escalation inappropriate

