For both **Part 1** and **Parts 2b** and **2e**, in the absence of a DLT, patients must complete the first cycle of treatment (28 days) in order to be considered evaluable for DLT. Patients who discontinue for any reason other than a DLT or Grade ≥ 2 toxicity and have received less than 21 of 28 days of dosing will not be considered evaluable for DLT and will be replaced; however, their data will be reviewed by the study committee and a decision will be made based on their review.

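### The synopsis and Section 9.3 define a transaminase DLT differently, and Section 9.3 gives conflicting rules on which early Cycle 1 stops count as DLT-evaluable

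*Protocol*

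**What the plan says.** **What counts as a DLT.** Both the synopsis and Section 9.3 treat related Grade 3 or higher non-hematologic toxicity in Cycle 1 as a DLT, with listed exceptions. The transaminase exception is worded differently in the two places.

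- Synopsis: "Grade 3 increases in transaminases confirmed upon repeat testing lasting" 5 days or less. It sets no condition on symptoms.
- Section 9.3: "Grade 3 asymptomatic increases in transaminases (AST, ALT) confirmed upon repeat testing which resolves" to Grade 2 or below in less than 5 days.

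**Who is evaluable.** Section 9.3 holds three statements.

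- "Subjects who withdraw from the study prior to completing Cycle 1 for any reason other than a DLT will be replaced".
- Without a DLT, "patients must complete the first cycle of treatment (28 days) in order to be considered evaluable for DLT".
- Those who stop for a reason that is neither a DLT nor Grade 2 or higher toxicity, and who "have received less than 21 of 28 days of dosing will not be considered evaluable for DLT", are replaced. For this group, "their data will be reviewed by the study committee and a decision will be made based on their review".

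The synopsis repeats the second and third statements and ends with "This will be evaluated by the Study Committee".

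**Where the count is used.** Section 9.2.2 escalates "If less than one-third of evaluable patients in a given cohort experiences a DLT", with 0 of 3 and at most 1 of 6 as examples. At one-third or more, the dose is declared intolerable and the MTD exceeded. The synopsis stopping rule halts dosing in a cohort of 6 with 2 or more DLTs. The MTD/RP2D is a primary endpoint of Part 1, and the RP2D of Parts 2b and 2e.

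**The concern.** The escalation rule is a fraction, and the protocol fixes neither part of it uniquely. The transaminase exception sets the numerator and the evaluability rule sets the denominator. In cohorts of 3 or 6, one reclassified patient can move the result across the one-third limit. Two people following the document could then reach different decisions on the same cohort.

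The conflict falls on a toxicity that the protocol itself expects. Section 5.6.1 calls hepatotoxicity an important reaction to PLX3397. Section 5.10 links sunitinib to transaminase increases and reports hepatocellular necrosis with PLX9486 in rodents at exposures likely to be reached. Nothing in the document says whether the synopsis or the body governs.

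**Working it through.** **1. Transaminase exception.** Each case is a drug-related Grade 3 rise in Cycle 1, confirmed on repeat testing.

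| Case | Synopsis | Section 9.3 |
|---|---|---|
| Asymptomatic, Grade 2 or below after 3 days | Exempt | Exempt |
| Symptomatic, Grade 2 or below after 3 days | Exempt | DLT |
| Asymptomatic, lasting exactly 5 days | Exempt | DLT |
| Lasting more than 5 days | DLT | DLT |

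The final catch-all in both lists does not close the gap, because it leaves out toxicities already excepted.

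**2. Evaluability.** Each case is a patient without a DLT who leaves the study. The Day 24 patient is taken to have been dosed without interruption.

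| Case | Replacement sentence | 28-day sentence | 21-of-28-day sentence |
|---|---|---|---|
| Day 10, neither DLT nor Grade 2 or higher toxicity | Replaced | Not evaluable | Not evaluable, replaced |
| Day 10, Grade 2 toxicity | Replaced | Not evaluable | Outside the non-evaluable group |
| Day 24, not a DLT | Replaced | Not evaluable | Outside the non-evaluable group |

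The last column is read by implication: being outside the non-evaluable group is taken to mean counted. On the other reading, everyone short of 28 days is non-evaluable anyway, and neither the 21-day threshold nor the Grade 2 exception has any effect.

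**3. The plan's own figures.** Tables 27, 29 and 30 give the probability of escalating at true DLT rate p. For 3+3 this is (1−p)³ + 3p(1−p)²·(1−p)³. At p = 0.30 it is 0.343 + 0.441 × 0.343 = 0.494. From 10% to 70% the formula gives 0.906, 0.709, 0.494, 0.309, 0.172, 0.082 and 0.032. The tables state 0.91, 0.71, 0.49, 0.31, 0.17, 0.08 and 0.03, so they are correct. They presuppose a single meaning of DLT and of evaluable patient.

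**4. Effect by count, with no assumed rates.**

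- (a) Six evaluable, one undisputed DLT, one contested transaminase rise: 1/6 = 17% under the synopsis, below one-third. Under Section 9.3 it is 2/6 = 33%, so the MTD is exceeded and dosing in the cohort stops.
- (b) Three patients, no DLT, one Day 24 withdrawal: 0/3 if the patient counts, which meets the DLT threshold for escalation. The Grade 2 condition and the requirement of 28 days' tolerability at the lower dose still apply. If the patient does not count, only 2 are evaluable and a replacement needs a further 28-day window.
- (c) Six patients, one DLT, one Day 24 withdrawal: 1/6 = 17% or 1/5 = 20%. Both are below one-third, but in the second case the MTD criterion, stated on 6 patients, waits for a replacement.
- (d) Part 1 at 1000 mg QD (Table 10): 1 DLT in 7 enrolled = 14%. Exclusions alone reach one-third only at 1/3, with 4 of the 7 non-evaluable. A hypothetical reclassified event gives 2/7 = 29%, or 2/6 = 33% with one exclusion as well. No such event is reported, and Table 10 gives numbers enrolled, not evaluable.

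**5. Effect on escalation under assumed rates.** The document gives no rates for contested cases, so these are illustrations.

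- If the Section 9.3 wording adds 2, 5 or 10 percentage points to the DLT rate, the probability of escalating falls from 0.709 to 0.665, 0.600 or 0.494 at a base rate of 20%. At 30% it falls from 0.494 to 0.454, 0.396 or 0.309.
- If 5%, 10% or 20% of patients leave early without a DLT and are counted rather than replaced, the rate per counted patient becomes p(1−w), where w is that share. At p = 0.30 the probability of escalating rises from 0.494 to 0.525, 0.557 or 0.622.

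**The case against.** The strongest reply is that the gap is narrow and other controls surround it. A Grade 3 rise lasting at most 5 days has presumably fallen to Grade 2 or below, so the recovery grade adds little. What remains is the symptom condition and the exact 5-day boundary. This stands, and both remaining differences are real.

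Contested rises would also attract attention anyway. A related Grade 3 rise is a related Grade 2 or higher toxicity, which already conditions planned escalation (Sections 9.2.1.1 and 9.2.1.2). Two such patients send the escalation increment to the study committee (Section 9.2.2). Table 22 requires a hold and discussion with the Medical Monitor for ALT or AST above 3 × ULN with listed symptoms. These controls reduce the risk, but none says whether the event counts as a DLT. Intolerability and the Cycle 1 cohort stop are tied to that count.

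On evaluability, the 21-of-28-day sentence may be meant to qualify the 28-day sentence, and the synopsis remark on committee review may cover both. That is a possible reading. It leaves the separate replacement sentence in conflict, and the remark supplies no counting rule. In Section 9.3 the committee review attaches to the group with under 21 days, not to the two disputed cases.

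Finally, no harm is shown. Part 1 is complete, and Section 5.5.1.1 bases the single-agent RP2D on exposure reaching the target range with little gain expected from a higher dose. The one reported DLT was anemia. This stands and limits the weight of the point. Part 1 example (d) is hypothetical.

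**Conclusion.** The concern holds and should be fixed. The transaminase exceptions contradict each other for a related symptomatic Grade 3 rise of up to 5 days and for one of exactly 5 days. The evaluability statements conflict for a non-DLT stop after 21 to 27 days of dosing and for an earlier stop for non-DLT Grade 2 or higher toxicity; that part rests on giving the 21-day threshold and the Grade 2 exception some effect.

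The consequence is a possible change of decision on a primary endpoint: 1/6 against 2/6 from one contested transaminase event, or 0/3 against only 2 evaluable patients from one Day 24 withdrawal. The frequency is unknown and may be low: the synopsis reports one DLT with 49 patients treated, 1/49 = 2%, and not all 49 need be DLT-evaluable. No past dose decision is shown to have been affected.

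**What to change.** - Reconcile the synopsis and Section 9.3 into one DLT list, worded identically in both places.
- Reconcile the evaluability and replacement statements in the synopsis and Section 9.3 into one rule. It should cover Cycle 1 stops for toxicity, stops for progression, and stops after 21 or more days of dosing. Cross-refer to the general, discretionary replacement rule in Section 10.4 so that the two agree.
- Check Cycle 1 transaminase events and early withdrawals in Parts 1, 2b and 2e against the reconciled rules, and report any DLT count that changes.
- Report the number evaluable beside the number enrolled. Table 12 shows the need for clear denominators: it lists 4 + 8 = 12 patients where the text of Section 5.5.1.2 gives 11.

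The choice of clinical threshold belongs to the sponsor and investigators. The cost is an amendment of wording and one check of data already held.

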9.3.1 Dose-limiting Toxicity Resulting in Death

In the event of a fatal DLT that is possibly or probably attributed to study drug, further accrual to that dose level will be suspended pending review by the Study Committee. The Study Committee (see [Section 10.1.1](#)) will review the available data regarding the event and provide recommendations.

9.4 Dose Modification Guidelines and Stopping Rules

Toxicities that occur outside the DLT window will be taken into consideration when determining the RP2D. Reduction/interruption of dosing for AEs may take place at any time. [Table 22](#) summarizes the guidelines for dosage modification (including stopping rules) for PLX9486-related toxicities as well as guidelines for their management. Dose reductions for PLX9486 should occur in decrements of 200 mg per day and for PLX3397 should occur in decrements of 200 mg/day, depending on the toxicity grade, as noted in [Table 21](#). [Table 23](#) summarizes the guidelines for dosage modification (including stopping rules) for PLX3397-related toxicities (excluding liver function abnormalities) and guidelines for their management. [Table 24](#) summarizes the guidelines for PLX3397 dosage modifications (including stopping rules) for liver function abnormalities, and [Table 25](#) provides additional liver evaluations for the management of liver function abnormalities.

Dose reductions of one or both study drugs will be made based on the known toxicity of PLX3397 and on the specific toxicity of PLX9486, and will be made only after decision by the Sponsor's medical monitor in discussion with the investigator(s). The dose modification guidelines in [Table 22](#) are applicable to all parts of the study. Dose modifications of sunitinib should follow the USPI, as well as the guidance below.

If a stable combination dose of PLX9486 and PLX3397 is unattainable, dosing will be halted and a new dose configuration with a lower dose of PLX3397 (e.g., 600 mg PLX3397 and 150 mg PLX 9486) will be developed. For the combination parts of the study (Part 2b and [redacted]), if one study drug needs to be temporarily discontinued due to an adverse event, then both drugs need to be discontinued until the adverse event resolves per the dose modification guidelines. If one study drug needs to be permanently discontinued, then both study drugs must be permanently discontinued and the patient taken off-study.

If a stable combination dose of PLX9486 and sunitinib is unattainable, dosing will be halted and a new dose configuration with a lower dose of sunitinib (e.g., 25 mg sunitinib and 150 mg PLX 9486) will be developed. For the combination parts of the study (Part 2e and [redacted]), if one study drug needs to be temporarily discontinued due to an adverse event, then both drugs need to be discontinued until the adverse event resolves per the dose modification guidelines. If one study drug needs to be permanently discontinued, then both study drugs must be permanently discontinued and the patient taken off-study.

These parameters are only a guide and are not intended to supersede the clinical judgment of the treating physician. The dose modification/reduction guidelines are for clinically significant toxicities that are at least possibly related to study drug administration. Definitions of "clinically significant" and "related" will be made based on the judgment of the investigator and the case discussed with the Medical Monitor as needed. All adjustments should be made in consultation with the Medical Monitor. Dosing interruptions longer than 2 weeks for any reason should generally result in discontinuation from the study, unless the patient has demonstrated a clinical benefit from therapy and would like to continue dosing with study drug after discussion between the investigator and the Sponsor.

Table 22: Recommended PLX9486 Dose Modifications (Including Stopping Rules)

All Drug-Related Toxicities	Frequency	When to Hold or Stop	When to Restart Dose ^a
Grade 3 or 4 neutropenia	1st Appearance	Interrupt until ANC recovers to $\geq 1 \times 10^9/L$; growth factor support permitted	If recovered to ANC $\geq 1 \times 10^9/L$ in ≤ 7 days, resume at same dose.
			If not recovered to ANC $\geq 1 \times 10^9/L$ after 7 days, reduce dose by 1 dose level.
		Interrupt until ANC recovers to $\geq 1 \times 10^9/L$; growth factor support permitted	If recovered to ANC $\geq 1 \times 10^9/L$ in ≤ 7 days, reduce dose by 1 dose level.
	2nd Appearance	Interrupt until ANC recovers to $\geq 1 \times 10^9/L$; growth factor support permitted	If recovered to ANC $\geq 1 \times 10^9/L$ in ≤ 7 days, reduce dose by 1 dose level.
			If not recovered to ANC $\geq 1 \times 10^9/L$ after 7 days, reduce dose by 2 dose levels.
	3rd Appearance	Interrupt until ANC recovers to $\geq 1 \times 10^9/L$; growth factor support permitted	If recovered to ANC $\geq 1 \times 10^9/L$ in ≤ 7 days, reduce dose by 1 dose level.
			If not recovered to ANC $\geq 1 \times 10^9/L$ after 7 days, discontinue permanently.
Grade 3 or 4 febrile neutropenia	1st Appearance	Interrupt until ANC and fever recover; provide growth factor support	If recovered to ANC $\geq 1 \times 10^9/L$ and T $\leq 38^{\circ}C$ in ≤ 7 days, reduce dose by 1 dose level.
			If not recovered to ANC $\geq 1 \times 10^9/L$ after 7 days, discontinue permanently.
	2nd Appearance	Interrupt until ANC and fever recover; provide growth factor support	If recovered to ANC $\geq 1 \times 10^9/L$ and T $\leq 38^{\circ}C$, reduce dose by an additional 1 dose level.
			If not recovered to ANC $\geq 1 \times 10^9/L$ after 7 days, discontinue permanently.
	3rd Appearance	Discontinue permanently; provide growth factor support	N/A

All Drug-Related Toxicities	Frequency	When to Hold or Stop	When to Restart Dose ^a
Grade 3 or 4 thrombocytopenia without bleeding	1st Appearance	Interrupt until PLT $\geq 75 \times 10^9/L$	If recovered to PLT $\geq 75 \times 10^9/L$ ≤ 7 days, resume at same dose.
			If not recovered to PLT $\geq 75 \times 10^9/L$ after 7 days, reduce dose by 1 dose level.
	2nd Appearance	Interrupt until PLT $\geq 75 \times 10^9/L$	If recovered to PLT $\geq 75 \times 10^9/L$ in ≤ 7 days, reduce dose by 1 dose level.
			If not recovered to PLT $\geq 75 \times 10^9/L$ after 7 days, reduce dose by 2 dose levels.
Grade 3 or 4 thrombocytopenia with bleeding	3rd Appearance	Interrupt until PLT $\geq 75 \times 10^9/L$	If recovered to PLT $\geq 75 \times 10^9/L$ in ≤ 7 days, reduce dose by 1 dose level.
			If not recovered to PLT $\geq 75 \times 10^9/L$ after 7 days, discontinue permanently.
	4th Appearance	Discontinue	N/A
	1st Appearance	Interrupt until PLT $\geq 75 \times 10^9/L$ and bleeding stops	If recovered to PLT $\geq 75 \times 10^9/L$ and bleeding stopped ≤ 7 days, reduce by one dose level. If not recovered to PLT $\geq 75 \times 10^9/L$ and bleeding continues discontinue permanently.
Other Grade 3 toxicities (excluding trans-aminase increases)	1st Appearance	Interrupt until resolved (Grade 0–1); start symptomatic treatment if possible	If recovered ≤ 5 days, resume at same dose.
			If symptoms persist for >5 days despite supportive management, reduce by 1 dose level.
	2nd Appearance	Interrupt until resolved (Grade 0–1); start symptomatic treatment if possible	If recovered ≤ 5 days, reduce dose by 1 dose level.
			If symptoms persist for >5 days despite supportive management, discontinue permanently.
Other Grade 4 toxicities (excluding trans-aminase increases)	1st Appearance	Interrupt until resolved (Grade 0–1); start symptomatic treatment if possible	If recovered <5 days, reduce by 1 dose level.
			If symptoms persist for ≥ 5 days despite supportive management, discontinue permanently.
	2nd Appearance	Discontinue permanently; start symptomatic treatment if possible	N/A

All Drug-Related Toxicities	Frequency	When to Hold or Stop	When to Restart Dose ^a
Transaminase increases	
 ALT or AST $>8 \times$ ULN ALT or AST $>5 \times$ ULN for more than 2 weeks ALT or AST $>3 \times$ ULN and Total bilirubin $>2 \times$ ULN or INR >1.5 (in absence of anticoagulation) ALT or AST $>3 \times$ ULN with the appearance of fatigue, nausea, vomiting, right upper quadrant pain or tenderness, fever, rash, and/or eosinophilia ($>5\%$). 	
Immediately hold dose and discuss with Medical Monitor.
 
Institute close monitoring. Any decision to restart after transaminases return to baseline must be discussed with the Medical Monitor.
	N/A
QTcF >500 msec or 60 msec increase from baseline verified on repeat ECG	First appearance	
Interrupt study drug until resolved.
	
Upon recovery to QTc ≤ 500 ms (Grade ≤ 2), restart at a reduced dose (at least one dose level).
 
Permanently discontinue study drug if the QTc interval remains >500 ms and increased >60 ms from pretreatment values (after controlling cardiac risk factors for QT prolongation e.g., electrolyte abnormalities, congestive heart failure, and bradyarrhythmias)^b.

Note: The guidelines in this table apply to all parts of the study.

^a See [Section 9.2](#) for dose levels.

^b QTc: Only one dose reduction is permitted per patient. Prior to and following treatment initiation or after dose modification of study drugs for QTc prolongation, evaluate ECG and electrolytes (including potassium, magnesium, and calcium) after 15 days, and monthly thereafter or more often as clinically indicated.

Reductions or interruptions of PLX3397 for toxicity may take place at any time during the study according to the guidelines in [Table 23](#), [Table 24](#), and [Table 25](#). Dose reduction/interruption guidelines for hematologic and nonhematologic treatment-related AEs are based on severity. Dose interruptions can be implemented at the discretion of the treating Investigator to manage intolerable or clinically significant toxicity. If a dose interruption is required, study assessments should be performed as scheduled, irrespective of the study drug delay, with the exception of PK

assessments, which should be deferred until treatment is resumed. Interruptions due to toxicity lasting >14 days require treatment discontinuation unless the medical monitor approves continuation.

Table 23: Recommended PLX3397 Dose Modifications (Including Stopping Rules and Excluding Transaminase Increases)

All Drug-Related Toxicities	Frequency	When to Hold or Stop	When to Restart Dose ^a
Grade 3 or 4 neutropenia	1st Appearance	Interrupt until ANC recovers to $\geq 1 \times 10^9/L$; growth factor support permitted	If recovered to ANC $\geq 1 \times 10^9/L$ in ≤ 7 days, resume at same dose.
			If not recovered to ANC $\geq 1 \times 10^9/L$ after 7 days, reduce dose by 1 dose level.
	2nd Appearance	Interrupt until ANC recovers to $\geq 1 \times 10^9/L$; growth factor support permitted	If recovered to ANC $\geq 1 \times 10^9/L$ in ≤ 7 days, reduce dose by 1 dose level.
			If not recovered to ANC $\geq 1 \times 10^9/L$ after 7 days, reduce dose by 2 dose levels.
Grade 3 or 4 febrile neutropenia	3rd Appearance	Interrupt until ANC recovers to $\geq 1 \times 10^9/L$; growth factor support permitted	If recovered to ANC $\geq 1 \times 10^9/L$ in ≤ 7 days, reduce dose by 1 dose level.
			If not recovered to ANC $\geq 1 \times 10^9/L$ after 7 days, discontinue permanently.
	4 th Appearance	Discontinue	
	1st Appearance	Interrupt until ANC and fever recover; provide growth factor support	If recovered to ANC $\geq 1 \times 10^9/L$ and T $\leq 38^{\circ}C$ in ≤ 7 days, reduce dose by 1 dose level.
			If not recovered to ANC $\geq 1 \times 10^9/L$ after 7 days, discontinue permanently.
Grade 3 or 4 thrombocytopenia without bleeding	2nd Appearance	Interrupt until ANC and fever recover; provide growth factor support	If recovered to ANC $\geq 1 \times 10^9/L$ and T $\leq 38^{\circ}C$, reduce dose by an additional 1 dose level.
			If not recovered to ANC $\geq 1 \times 10^9/L$ after 7 days, discontinue permanently.
	3rd Appearance	Discontinue permanently; provide growth factor support	N/A
	1st Appearance	Interrupt until PLT $\geq 75 \times 10^9/L$	If recovered to PLT $\geq 75 \times 10^9/L$ in ≤ 7 days, resume at same dose.
			If not recovered to PLT $\geq 75 \times 10^9/L$ after 7 days, reduce dose by 1 dose level.
		Interrupt until PLT $\geq 75 \times 10^9/L$	If recovered to PLT $\geq 75 \times 10^9/L$ in ≤ 7 days, reduce dose by 1 dose level.
	2nd Appearance	Interrupt until PLT $\geq 75 \times 10^9/L$	If not recovered to PLT $\geq 75 \times 10^9/L$ after 7 days, reduce dose by 2 dose levels.
	3rd Appearance	Interrupt until PLT $\geq 75 \times 10^9/L$	If recovered to PLT $\geq 75 \times 10^9/L$ in ≤ 7 days, reduce dose by 1 dose level.

All Drug-Related Toxicities	Frequency	When to Hold or Stop	When to Restart Dose ^a
			If not recovered to PLT $\geq 75 \times 10^9/L$ after 7 days, discontinue permanently.
			4 th Appearance Discontinue
Grade 3 or 4 thrombocytopenia with bleeding	1st Appearance	Interrupt until PLT $\geq 75 \times 10^9/L$ and bleeding stops	If recovered to PLT $\geq 75 \times 10^9/L$ and bleeding stopped ≤ 7 days, reduce by one dose level. If not recovered to PLT $\geq 75 \times 10^9/L$ and bleeding continues discontinue permanently.
Other Grade 3 toxicities (excluding trans-aminase increases)	1st Appearance	Interrupt until resolved (Grade 0–1); start symptomatic treatment if possible	If recovered ≤ 5 days, resume at same dose. If symptoms persist for >5 days despite supportive management, reduce by 1 dose level.
			If symptoms persist for >5 days despite supportive management, discontinue permanently.
	3rd Appearance	Discontinue permanently; start symptomatic treatment if possible	N/A
Other Grade 4 toxicities (excluding trans-aminase increases)	1st Appearance	Interrupt until resolved (Grade 0–1); start symptomatic treatment if possible	If recovered <5 days, reduce by 1 dose level. If symptoms persist for ≥ 5 days despite supportive management, discontinue permanently.
			N/A
QTcF >500 msec or 60 msec increase from baseline verified on repeat ECG	First appearance	Interrupt study drug until resolved.	Upon recovery to QTc ≤ 500 ms (grade ≤ 2), restart at a reduced dose (at least one dose level). Permanently discontinue study drug if the QTc interval remains >500 ms and increased >60 ms from pretreatment values (after controlling cardiac risk factors for QT prolongation e.g., electrolyte abnormalities, congestive heart failure, and bradyarrhythmias) ^b .

Note: The guidelines in this table apply to all parts of the study.

^a See [Section 9.2](#) for dose levels.

^b QTc: Only one dose reduction is permitted per patient. Prior to and following treatment initiation or after dose modification of study drugs for QTc prolongation, evaluate ECG and electrolytes (including potassium, magnesium, and calcium) after 15 days and monthly thereafter or more often as clinically indicated.

Table 24: PLX3397 Dose Modification Guidelines for Liver Function Abnormalities or Bilirubin Increases

Toxicity Grade CTCAE v0.4	Initial Action	Outcome	Action
ALT or AST Grade 2 ($>3\text{--}5 \times \text{ULN}$); No increase in bilirubin ^a	Re-check ALT and AST immediately Hold study drug Monitor weekly ^b Check for changes to medications and for symptoms	Resolution to Grade 0–1 or baseline (no bilirubin increase)	Restart on resolution Grade 0–1 or baseline at 1 dose lower (reduce by one 200 mg capsule)
Grade 3 ALT or AST increase ($>5\text{--}20 \times \text{ULN}$); No increase in bilirubin ^a	Re-check ALT and AST immediately Hold study drug Monitor 2x/week ^b Check for changes to medications and for symptoms	Resolution to Grade 0–1 or baseline (no bilirubin increase) within 14 days	Restart on resolution to Grade 0–1 or baseline at 1 dose lower (reduce by one 200 mg capsule)
		ALT and AST not decreasing within 14 days of holding study drug	Proceed to liver evaluation as outlined in Table 25 . Restart only on resolution to Grade 0–1/baseline at 1 dose lower (reduce by one 200 mg capsule); For max AST or ALT $>8 \times \text{ULN}$, consult with medical monitor prior to re-start
Grade 4 ALT or AST ($>20 \times \text{ULN}$)	Discontinue treatment Monitor 2x/week until resolution to Grade 2 Follow-up until resolution Grade 0–1 or baseline Check for changes to medications and for symptoms	All outcomes	Discontinue treatment; Proceed to liver evaluation as outlined in Table 25 . If clear confirmed alternate cause, restart on resolution to Grade 0–1 or baseline at 1 dose lower (reduce by one 200 mg capsule)
Any grade ALT or AST increase ^a with any bilirubin increase or signs of hypersensitivity	Discontinue treatment Monitor 2x/week until resolution to Grade 2 Follow-up until resolution Grade 0–1 or baseline Check for changes to medications and for symptoms	All outcomes	Discontinue treatment; Proceed to liver evaluation as outlined in Table 25 . If clear confirmed alternate cause, restart on resolution to Grade 0–1 or baseline at 1 dose lower (reduce by one 200 mg capsule)

ALT = alanine aminotransferase; AST = aspartate aminotransferase;

CTCAE = Common Terminology Criteria for Adverse Events; ULN = upper limit of normal

^a An increase in bilirubin is defined as all of the following: total bilirubin $>\text{ULN}$, total bilirubin $>20\%$ above baseline, and direct bilirubin $>\text{ULN}$. If all of these conditions are met, then bilirubin is considered increased and should be immediately re-checked. PLX3397 treatment should be immediately discontinued for increased bilirubin unless and until there is a clear, confirmed alternate cause.

^b If ALT, AST, or bilirubin worsens during the monitoring period, follow the applicable guidance for the worst toxicity grade.

Table 25: PLX3397 Additional Liver Evaluation

Evaluation	Comments
Increase frequency of testing liver chemistries to twice per week, including INR, and continue until liver chemistries have stabilized, and then reduce to weekly until liver chemistries return to normal or baseline.	Investigational treatment may be started after liver function tests recover to Grade 0 to 1 or baseline level, and in consultation with Medical Monitor.
Detailed history focusing on medications and substances used: alcohol, change in medication dosages, new medications added, attention to use of acetaminophen, OTC medication use, and recreational drug use. Check for change in diet or use of dietary supplements, with particular attention to dose and duration of any herbal product.	Suspect medications will be discontinued or substituted for if possible.
Detailed medical history and physical examination seeking new abnormalities.	Evaluate abnormalities found.
Full serological evaluation for hepatitis A, B, C, and E (IgG and IgM). Check for autoimmune hepatitis with serological laboratory studies.	If viral hepatitis or autoimmune hepatitis suggested, have patient evaluated by hepatologist.
Liver ultrasound performed to evaluate liver and biliary tree.	Evaluate any abnormalities found.
Check history for exposure to chemical agents.	Remove chemical exposure and have patient seen by hepatologist.
Obtain hepatology consult if liver function continues to rise beyond 14 d.	Contact Medical Monitor.
We request that cases be discussed with the Medical Monitor as defined in the protocol whenever investigational product is being held for liver function test abnormality.	

Ig = Immunoglobulin; INR = international normalized ratio; OTC = over-the-counter

For suspected cases of cholestatic liver injury (e.g., aminotransferase increase concurrent with hyperbilirubinemia, or liver biopsy suggesting cholestasis and/or ductopenia), patients will be followed to assess long-term outcome. Additional diagnostic and follow-up procedures might be implemented as appropriate to fully assess the event.

Sunitinib Dose Modification Guidelines:

For all sunitinib drug modifications, see [Section 9.2.4](#). For further guidance, consult the package insert.

